1.2. Schema

Figure 1: Study Schematic

- Participants eligible for the study will be enrolled on Day -7 and initiated on a copper- and molybdenum-controlled diet, which will be continued during Treatment Period 1 and Treatment Period 2 when in the CRU, through Day 39.
- Participants will be admitted to the CRU for Treatment Period 1 on Day -8 and may be discharged on Day 9 or remain in the CRU for their own safety or to maintain the integrity of the conduct of the study. Participants who are discharged will be re-admitted on Day 22 or Day 23 for Treatment Period 2 and will remain in house until Day 40. To ensure flexibility, the Outpatient Period may be extended up to an additional 14 days with Investigator approval. In this situation, participants will be given additional investigational product to support daily dosing throughout the Outpatient Period. In such cases, the actual Outpatient Period duration will be recorded and the participant will continue Inpatient Period 2 at Day 23.
- Participants will be administered ALXN1840 at a dose of 15 mg/day on Day 1 through Day 28 and then increase to 30 mg/day on Day 29 through Day 39. During the Outpatient Period, participants will use SMS text messaging to confirm study intervention administration.
- Participants will have 3 intake and output collection periods including:
 - Baseline Day -4 through Day -1
 - Day 1 through Day 8 (I/O for 15 mg)
 - Day 25 through Day 39 (Days 25 through 28, I/O for 15 mg; Days 29 through 39, I/O for 30 mg)
- During these periods all intake (including food and drink) and output (including urine and feces) will be collected and assessed for copper and molybdenum.
- Blood sampling for PK/PD will be as follows:
 - PK/PD collection (24-hour): Days 1, 25, 29, and 39
 - Pre-dose PK/PD sampling days: Days 4 - 7, Days 26 - 28, Days 30 - 38
 - End of Study Visit Day 54 +/- 2 days

Abbreviations: AP = accumulation period; CRU = clinical research unit; EOS = End of Study; I/O = input/output; PD = pharmacodynamic; PK = pharmacokinetic; SS = steady state.

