1.3. Schedule of Activities (SoA)

Table 1: Schedule of Activities

Study Procedures	Screening ^a		C-I ^b																		UNS ^d	EOS or ET ^e			
	Screening	C-I	C-I	Inpatient Period 1							OP ^c	Inpatient Period 2													
Days	-42 to -9	-21	-8	-7	-6 through -5	-4 through -1	1	2-3	4-7	8	9	10-22	23	24	25	26-28	29	30-35	36	37-38	39	40		EOS Day 54+/-2	
Eligibility																									
Informed consent	X																								
Admit to unit			X										X												
Discharge from unit ^f											X											X			
Outpatient visit or phone call												X ^g													
Inclusion/exclusion	X		X				X																		
Discuss/document contraception	X		X								X														X
Follicle-stimulating hormone (post-menopausal females only ^h)	X																								
Alcohol test	X		X																						
Urine drug screen	X		X																						
HIV, hepatitis B and C screen	X																								
Study Administration																									
Medical history/demographics ⁱ	X																								
WD history ^j	X																								
Prior WD treatment ^j	X						X																		
Physical examination ^k	X		X									X													X
Height ^l , weight, and BMI	X		X									X										X			
Enrollment																									
Enrollment/inclusion				X																					
Discontinue chelation therapy						X																			→
Discontinue zinc therapy		X																							→
Administration of Study Intervention^m																									
ALXN1840 15 mg/day							X	X	X	X	X	X	X	X	X	X									
ALXN1840 30 mg/day																	X	X	X	X	X				
Study intervention compliance											X ⁿ	X													
PK/PD Analyses^o																									
Blood sampling for PK: Plasma total Mo and PUF-Mo							X ^p	X						X ^p	X	X ^p	X	X	X	X	X ^p	X			

Study Procedures	Screening ^a		C-I ^b																		UNS ^d	EOS or ET ^e			
	Screening		C-I	Inpatient Period 1							OP ^c	Inpatient Period 2													
Days	-42 to -9	-21	-8	-7	-6 through -5	-4 through -1	1	2-3	4-7	8	9	10-22	23	24	25	26-28	29	30-35	36	37-38	39	40		EOS Day 54+/-2	
PD: Plasma total and PUF-Cu, LBC, ceruloplasmin, ceruloplasmin-bound Cu																									
Safety Assessments / Laboratory Analyses																									
Chemistry ^g , hematology, Coagulation	X		X			X ^r				X		X ^g	X			X ^r		X				X		X	
Urinalysis	X		X							X		X ^g	X			X						X		X	
Urine/serum pregnancy test ^s	X		X									X												X	
Retained serum sample (safety) ^f				X																					

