Vitals sign measurements ^h	X			X			X				X		X									X		X	
12-lead ECG (triplicate)	X			X			X				X		X									X		X	
Adverse events	X		X	X	X	X	X	X	X	X	X	X	X	X	X	X	X	X	X	X	X	X	X	X	
Balance assessments																									
Cu/Mo-controlled meals ^v				X	X	X	X	X	X	X			X	X	X	X	X	X	X	X	X	X			
Light exercise regimen				X	X	X	X	X	X	X		X	X	X	X	X	X	X	X	X	X	X			
Urination and bowel movement monitoring, menstruation check ^s						X	X	X	X	X					X	X	X	X	X	X	X	X			
24-hour urine for Cu and Mo ^w						X	X	X	X	X					X	X	X	X	X	X	X	X			
Feces for Cu and Mo ^x						X	X	X	X	X					X	X	X	X	X	X	X	X			
Other																									
Concomitant medication and non-pharmacologic therapy/procedure	X		X	X	X	X	X	X	X	X	X	X	X	X	X	X	X	X	X	X	X	X		X	

^a Within 42 days of ALXN1840 administration. Details of procedures that may be performed by sites designated as “screening sites” (only in the US) are detailed in Section 8.

^b Participants will be admitted to the clinical research unit (CRU) at least 10 hours prior to enrollment and initiation of copper- and molybdenum-controlled diet.

^c At the CRU’s discretion, participants may remain in the CRU or be readmitted on Day 22 with all procedures starting on Day 23.

^d Unscheduled study visits may occur at any time during the study and may include any study procedure as deemed necessary by the Investigator.

^e Participants are required to return to the CRU Day 54+/-2; participants will be discontinued from ALXN1840 medication by their physician at the latest by the Day 54 follow-up.

^f Discharge from the unit may occur after completion of all procedures on Day 9 and on Day 40 and after the Investigator has reviewed all safety assessment (including safety laboratory tests) and confirmed that the participant is appropriate for discharge.

^g A single outpatient visit or phone call and safety laboratory assessment should occur between Day 14 and Day 18. A phone call may take place on a different day than the blood draw within the Day 14 through Day 18 period.

^h If needed to confirm menopause.

- ⁱ Parameters include age and sex. Race and ethnicity will be collected where permitted by local regulations.
- ^j Wilson disease history will include diagnosis date, method of diagnosis, history of cirrhosis, details of any previous liver biopsies performed, and treatment received.

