- ^k A full physical examination will be performed at Screening, at check-in for the study, and at the End of the study/Early Termination Visit. A physical examination should also be performed on any participants with ongoing adverse events prior to discharge from the unit. Otherwise, a symptom-driven physical examination may be performed at other times, at the Principal Investigator's discretion.
- ^l Height at screening only.
- ^m While in the CRU, study intervention will be administered after an overnight fast (ie, at least 10 hours) at the same time every morning; drug is to be administered with 240 mL of water and meals should be delayed a minimum of 2 hours after dosing. As an outpatient, participants are expected to take ALXN1840 at approximately the same time daily (+/-1 hour). Participants should take the medication with a glass of water on an empty stomach; meals should be delayed a minimum of 2 hours after dosing.
- ⁿ During the outpatient period, participants will use SMS text messaging to confirm study intervention administration.
- ^o Blood sampling for PK/PD will occur before ALXN1840 administration and represents a predose trough. See [Table 2](#) for PK/PD sampling on Days 1, 25, 29, and 39.
- ^p PK/PD collection will include timepoints described in the schedule of PK/PD assessment for Days 1, 25, 29, and 39 ([Table 2](#)).
- ^q Samples for serum chemistry will be obtained following a fast of at least 8 hours at the Screening Visit and at check-in. In case of rechecks, and postdose serum chemistry, participants may not have fasted for 6 or 8 hours before the serum chemistry sample is taken.
- ^r Laboratory assessment including chemistry, hematology, and coagulation parameters should be performed on Days -8, -1, 8, 23, and 28 only.
- ^s Menstruation check is for women only; women of childbearing potential should only be enrolled after a negative serum pregnancy test result at Screening. Additional urine pregnancy testing will be standard for the protocol unless serum testing is required by site policies, local regulation, or Institutional Review Boards (IRBs)/Independent Ethics Committees (IECs) (Section 10.2). In addition to pregnancy tests detailed at the visits in the SoA, females of childbearing potential will be required to perform urine pregnancy tests at least every 4 weeks at their home or the study site throughout their time in the study.

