2.3.1. Risk Assessment

Details of the potential risks and mitigation strategy are provided in [Table 3](#).

Table 3: Potential Risks and Mitigation Strategy

Potential Risk of Clinical Significance	Summary of Data/Rationale for Risk	Mitigation Strategy
ALXN1840		
Dose-dependent elevations in transaminases (ALT and AST)	Generally mild to moderate in severity, asymptomatic and reversible with dose adjustments were reported, usually after 3 - 6 weeks of treatment. Results obtained from studies of ALXN1840 and ammonium tetrathiomolybdate in participants with WD; see the IB.	Regular monitoring of liver function tests. Dose modification or discontinuation (Section 6.6).
Anemia	Anemia has been observed in participants with WD, attributed to overtreatment and resultant copper depletion; see the IB.	Monitoring complete blood count. Dose modification or discontinuation (Section 6.6).
Low white blood cell count (leukopenia, bone marrow toxicity)	Leukopenia and bone marrow toxicity (myelosuppression) have been observed in participants with WD, attributed to overtreatment and resultant copper depletion. Results obtained from studies of ALXN1840 and ammonium tetrathiomolybdate in participants with WD; see the IB.	Monitoring of complete blood count. Dose modification or discontinuation (Section 6.6).
Neurological dysfunction	Neurological worsening may occur due to copper mobilization. Peripheral neuropathy may be seen with over decoppering; however, symptoms such as myelosuppression is typically seen earlier.	Regular monitoring for neurologic adverse events. Dose modification or discontinuation (Section 6.6).
Study Procedures		
Risks associated with the study design and procedures	Participants will undergo repeated blood draws to measure the PK of the study intervention and metabolism. Blood draws may result in ecchymosis, redness, and minor pain to the site. On rare occasion, infection or thrombophlebitis can occur.	Blood draws are optimized for PK. A cannula may be placed to minimize needle sticks; however, a catheter may not be left in place for longer than 72 hours and should be flushed a minimum of every 8 hours.

Abbreviations: ALT = alanine aminotransferase; AST = aspartate aminotransferase; IB = Investigator's Brochure; PK = pharmacokinetics; WD = Wilson disease.

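### A Schedule of Activities footnote gives what reads as a complete list of safety-laboratory days, and it conflicts with another footnote and with half the marks in its own row

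*Protocol*

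**What the plan says.** All the scheduling text is in Protocol 1.3, Table 1 and its footnotes.

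- Footnote r: "Laboratory assessment including chemistry, hematology, and coagulation parameters should be performed on Days -8, -1, 8, 23, and 28 only".
- Footnote g: "A single outpatient visit or phone call and safety laboratory assessment should occur between Day 14 and Day 18".
- The row for chemistry, "hematology, Coagulation" has marks in ten columns: Screening, Day -8, Days -4 to -1, Day 8, Days 10-22, Day 23, Days 26-28, Days 30-35, Day 40 and End of Study (Day 54). Superscript r appears on two of these, Days -4 to -1 and Days 26-28. Superscript g appears on Days 10-22.
- Footnote q gives a fasting rule for the serum chemistry sample at Screening, so it presupposes a draw that footnote r does not list.

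On dosing, Protocol 1.2 has participants take 15 mg/day through Day 28, "then increase to 30 mg/day on Day 29 through Day 39". On risk, Protocol 2.3.1 (Table 3) describes dose-dependent transaminase elevations, "usually after 3 - 6 weeks of treatment", and gives as mitigation "Regular monitoring of liver function tests".

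The body text does not settle which list applies. Protocol 8.2.4 refers to the Schedule of Activities for the timing and frequency of laboratory tests. Protocol 8 makes adherence to that schedule mandatory and rules out waivers.

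**The concern.** A footnote meant only to pick a day inside a multi-day column would need to name two days, -1 and 28. This one also names Days -8, 8 and 23, which have single-day columns and need no clarification, and it closes the list with the word *only*. It therefore reads as the complete set of draw days, and that set disagrees with the table it annotates.

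Three things depend on which list a site follows.

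- **Safety monitoring.** The ALT, bilirubin, hemoglobin, platelet and neutrophil criteria in Table 7 act on these results. The Safety Review Committee's planned review before the dose increase covers data through Day 23, so it cannot inform on the 30 mg days.
- **Deviations.** A site that draws on Day 40 departs from footnote r. A site that does not draw departs from the row. Both can say they followed the schedule.
- **Analysis.** Protocol 9.4.3 and SAP 7.3.3.1 plan laboratory shift tables by treatment, to the worst post-dose grade. Describing 30 mg requires results from that period. SAP 9.2.8 also takes its visit windows from the Schedule of Activities.

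**Working it through.** The plan states no figure to reproduce. The check sets the row against the footnote.

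| Column marked in the row | Superscript | In footnote r's list? |
|---|---|---|
| Screening | none | no |
| Day -8 | none | yes |
| Days -4 to -1 | r | yes, as Day -1 |
| Day 8 | none | yes |
| Days 10-22 | g | no |
| Day 23 | none | yes |
| Days 26-28 | r | yes, as Day 28 |
| Days 30-35 | none | no |
| Day 40 | none | no |
| End of Study (Day 54) | none | no |

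**Agreement.** 10 columns are marked. Footnote r accounts for 5 and omits 5.

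**30 mg period.** Days 29 through 39 are 39 - 29 + 1 = 11 dosing days. Days in footnote r's list that fall in this range: 0. Days in its list on or after Day 29: 0. The last listed draw is Day 28, the last day at 15 mg, and End of Study is 54 - 28 = 26 days later. By the row marks there are three later draws: one in the Days 30-35 column, one on Day 40 and one at End of Study.

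**Transaminase window.** Three to six weeks is 3 × 7 = 21 to 6 × 7 = 42, so Days 21 through 42, or 42 - 21 + 1 = 22 days. The part after Day 28 is 42 - 29 + 1 = 14 days, and 14/22 = 63.6%, about 64%.

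**Sensitivity to the Outpatient Period.** Days are nominal, because Protocol 4.1 allows that period to be extended by up to 14 days with the participant resuming at Day 23. With an extension of e days, nominal Day 28 falls on treatment day 28 + e, and 14 - e of the 22 window days come after it. That is 14 with no extension and 0 with the full 14 days. The literal gap between the Day 8 and nominal Day 23 draws then grows from 15 to 29 days, and footnote g's assessment is the one that would fall in it. The zero count for the 30 mg days does not depend on e.

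**Visit windows.** SAP 9.2.8 sets a lower bound of ceiling(target - (target - previous target)/2). For vital signs at Day 40 this gives ceiling(40 - 17/2) = 32, as in SAP Table 3. If footnote r's list supplied the laboratory target days, the last window would open at ceiling(28 - 5/2) = 26 with no upper limit. Results at 15 mg and at 30 mg would then fall in one window.

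**The case against.** The strongest reply is that no site would read footnote r as removing laboratory tests. The superscript sits on two multi-day cells, and naming a day within each is its natural function. The later marks are plain and carry no r. Protocol 8 requires sites to follow the schedule, so a site that does so draws after Day 28. The omission of Screening supports this, since footnote q assumes a chemistry sample there and so footnote r's list cannot have been meant as complete. This stands as an account of intent. A reader might infer that the trial was designed without laboratory monitoring at 30 mg, and the documents do not support that. The reply does not repair the wording, however. Footnotes r and g still conflict sentence against sentence, and the one multi-day mark in the 30 mg period has no footnote naming its day.

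A reader might also infer that footnote f contradicts footnote r, because discharge on Day 9 and Day 40 may occur only "after the Investigator has reviewed all safety assessment (including safety laboratory tests) and confirmed that the participant is appropriate for discharge". It does not. Footnote f requires a review, not a draw on the day of discharge. Day 9 has no mark in the laboratory row, so the Day 8 draw evidently serves that discharge. For Day 40, the conflict comes from the mark in the row.

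Two limits apply. First, the marks and superscripts were read from the PDF's text, where some superscripts on row labels are visibly garbled, so the cells carrying r and the Days 30-35 column should be confirmed on the printed table. If that mark belongs to the adjacent Day 36, it is still at 30 mg and still outside footnote r's list. The conflict between footnotes r and g does not depend on the table layout. Second, monitoring does not cease even on the literal reading. Urinalysis has its own row, not tagged r, with Day 40 and End of Study marks. Footnote d allows any procedure at an unscheduled visit. Table 7 requires weekly repeat testing once most of its laboratory criteria are met, and Protocol 8.2.4 requires clinically significant abnormal values to be repeated. None of these replaces a scheduled draw for finding a first abnormality.

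**Conclusion.** Footnote r is wrong as written. It is an internal inconsistency in safety-monitoring text, and nothing elsewhere in the protocol resolves it. Severity is minor to moderate: the probable intent is benign and the row marks show draws after Day 28, but the sentence as it stands permits the opposite.

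The consequence, 0 of 11 days at 30 mg and 14 of 22 window days without a scheduled chemistry, hematology or coagulation draw, holds only under the literal reading. The 14 of 22 also assumes that the Outpatient Period is not extended and that weeks are counted from Day 1. It measures what the wording allows and does not predict what sites will do.

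**What to change.** Reconcile footnote r with footnote g and the marks in the chemistry, hematology and coagulation row, so that the Schedule of Activities gives one unambiguous list of laboratory days. The reconciliation should include the multi-day mark in the 30 mg period, which at present has no stated day. Which days are right is for the sponsor and investigators to decide, and none is proposed here. Once the list is settled, confirm that the laboratory visit windows under SAP 9.2.8 use the same target days.

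The cost is one footnote, in the next amendment or an administrative letter. The analysis methods do not change.

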2. INTRODUCTION

ALXN1840 (bis-choline tetrathiomolybdate; formerly known as WTX101) is a novel copper binding agent in development for the treatment of WD.

2.1. Study Rationale

The principal aim of this exploratory study is to investigate the effects of ALXN1840 on copper balance in participants with WD. The study will specifically evaluate the effects of 2 different ALXN1840 dose levels as well as the duration of treatment on copper balance to further elucidate the dose response of “decoppering” versus “maintenance” dose in participants with WD.

ALXN1840 contains the active anion tetrathiomolybdate and has been shown to cause negative copper balance when administered to healthy animals as well as decopper the liver in animal models of WD (Mills, 1981; Czachor, 2002). In Study WTX101-201, which assessed the safety and efficacy of ALXN1840 in participants with WD, ALXN1840 demonstrated enhanced copper control as measured by reduced plasma $NCC_{corrected}$ for the stable tetrathiomolybdate-copper-albumin TPC (Weiss, 2017).

Depletion of copper by ALXN1840 has been shown to occur primarily through fecal elimination in both healthy and WD animal models. Sheep injected with 30 mg/day of tetrathiomolybdate for 5 days were shown to have an elevation of fecal copper during the treatment period increasing from a baseline of approximately 3 mg/day up to approximately 7 mg/day during the treatment period, before returning to baseline concentrations (Mason, 1988). Similarly, when Long-Evans Cinnamon (LEC) WD model rats were injected intraperitoneally with a saline solution of tetrathiomolybdate at a dose of 10 mg/kg body weight for 8 consecutive days, the amounts of both copper and molybdenum excreted into the feces increased significantly (Ogra, 2000), which may suggest that copper is excreted in a complex with tetrathiomolybdate into the feces. While fecal copper increases with tetrathiomolybdate, the amount of copper excreted into the urine decreased and that of molybdenum increased significantly during treatment with tetrathiomolybdate. Molybdenum in the urine was molybdate which does not bind copper (data on file). These findings are in line with other studies showing enhanced biliary and/or fecal excretion of copper and molybdenum upon administration of tetrathiomolybdate in rats and sheep (Komatsu, 2000; Ogra, 1995; Mason, 1988).

We hypothesize that repeated doses of ALXN1840 may drive a net negative copper balance in participants with WD by increasing fecal excretion of copper. In this study, copper balance will be calculated as the difference between measured copper input in food and drink and measured copper output in urine and feces. This method is classically considered the most objective measure of decoppering ability with a decoppering agent able to drive a net negative copper balance (Hill, 1986; Strickland, 1971; Walshe, 1973). The purpose of this study is to provide additional descriptive characterization of the effect of ALXN1840 on copper balance in participants with WD. Further data obtained may help support characterization of a “decoppering” versus “maintenance” dose of ALXN1840, where a decoppering dose would be a dose sufficient to drive a net negative copper balance and maintenance would support a more neutral copper balance.

The secondary aim of the study is to characterize the steady-state ADME (mass balance) of total molybdenum as a surrogate measure of ALXN1840 disposition in participants with WD. To confirm that steady state is adequately characterized by the plasma PK, a molybdenum mass balance assessment will be performed on Day 25 through Day 28 for the 15 mg/day dose and Day 36 through Day 39 for the 30 mg/day dose: if steady state is achieved, molybdenum(out) will equal molybdenum(in).

2.2. Background

ALXN1840 has been selected for development in WD due to its improved stability properties over ammonium tetrathiomolybdate, which has previously been studied in participants with WD and other indications. Ammonium tetrathiomolybdate and bis-choline tetrathiomolybdate nonclinical and clinical data reported to date support the efficacy and safety of ALXN1840.

ALXN1840 rapidly forms stable tetrathiomolybdate-copper-albumin TPCs, which stabilize free copper leading to a reduction in the NCC concentrations after correction for free copper bound to TPC ($NCC_{corrected}$).

Studies in both healthy and WD animal models showed that treatment with tetrathiomolybdate results in removal of copper from the liver. Tetrathiomolybdate administered to healthy mice by intraperitoneal injection resulted in a dose-dependent reduction in liver copper concentration over a treatment range of 0 - 6 mg/kg/day (human equivalent dose [HED] by body surface area [BSA] scaling: 0 - 1 mg/kg/day). The results of these studies indicated that only 30% - 40% of copper remained after 5 weeks of treatment. Similar liver decoppering (approximately 40% - 60%) was also reported in toxic milk mice (a WD animal model) at 5 mg/kg/day for 14 days (HED by BSA scaling: 0.4 mg/kg/day; Mills, 1981; Czachor, 2002). In LEC WD model rats, 25 mg/kg/day of ALXN1840 (HED by BSA scaling: 4 mg/kg/day) administered by oral gavage for 10 days, resulted in an approximately 50% decrease in liver copper concentration. Because ALXN1840 has been shown to have a similar mechanism of action in healthy and WD animal models, a mechanism of action study in healthy participants is being performed (Study ALXN1840-HV-108) to demonstrate that ALXN1840 can result in a change from baseline in copper balance with repeat-dose ALXN1840 (30 mg/day) treatment.

In the Phase 2 proof-of-concept Study WTX101-201 in participants with WD, ALXN1840 demonstrated a sustained control of free copper as measured by $NCC_{corrected}$. Importantly, ALXN1840 treatment resulted in improvements in disability and neurologic symptoms as measured by the Unified Wilson Disease Rating Scale (UWDRS, Parts II and III) and stabilization of liver function (Weiss, 2017). Treatment with ALXN1840 resulted in an acceptable safety and tolerability profile when initiated at 15 mg daily with Investigator-driven, individual participant titration of dose based on safety, $NCC_{corrected}$, and symptoms.

Following single-dose administration of 60 mg ALXN1840, total molybdenum peaked at approximately 4.54 hours with a terminal elimination half-life measured at approximately 51 hours. In Study WTX101-201, the PK of ALXN1840, based on total molybdenum, indicated that exposure in participants with WD at a dose of 30 mg appeared consistent with previous results from healthy participants. The half-life was estimated to be approximately 24 hours at steady state on Days 84 and 168 and was shorter than estimated in previous studies. Based on a total molybdenum PK half-life of approximately 24 - 51 hours, total molybdenum steady state may conservatively be reached within approximately 10 - 12 days. Nevertheless, results (as

measured by total molybdenum) obtained from the ALXN1840 balance study in the LEC WD rat model suggested that approximately 30% of a single dose of ALXN1840 remained in the liver by Day 7, indicating the possibility of tissue accumulation, particularly in the setting of high liver copper concentration ([Plitz, 2019](#)).

If the half-life of ALXN1840 in liver were longer than that of the systemic compartment, the accumulation may not be readily detected in the absence of a longer treatment period and with characterization of the terminal elimination period. An alternative approach to assessing steady state using total molybdenum PK is to assess whether the total molybdenum intake is equal to the total molybdenum output; this approach may detect any significant ongoing accumulation in the liver or other tissues.

Detailed descriptions of the chemistry, pharmacology, efficacy, and safety of ALXN1840 are provided in the Investigator's Brochure (IB).

